### 4.3 Lifestyle Considerations

No restrictions pertaining to lifestyle and/or diet will apply during the study.

### 4.4 Screen Failures

Screen failures are defined as participants who consent to participate in the study but are not subsequently randomly assigned to study intervention. A minimal set of screen failure information is required to ensure transparent reporting of screen failure participants to meet

---

the Consolidated Standards of Reporting Trials (CONSORT) publishing requirements and to respond to queries from regulatory authorities. Minimal information includes demography, screen failure details, eligibility criteria, and any non-treatment-emergent serious adverse event (SAE).

Subjects who do not meet the criteria for participation in this study (screen failure) may be rescreened once.

## 4.5 Rationale for Gender Distribution

No randomization stratified by gender is planned. All potential subjects will be asked for informed consent for participation in the study regardless of their gender. Because more women than men are affected by HS, a 2:1 distribution of women and men is expected to be enrolled in the study.

## 5 STUDY INTERVENTION

Study intervention is defined as any investigational intervention(s), marketed product(s), placebo, or medical device(s) intended to be administered to a study participant according to the study protocol.

All IMP supplied by the sponsor for use in this study will have been manufactured, tested, and released according to the standards of Good Manufacturing Practice.

### 5.1 Investigational Medicinal Product

#### 5.1.1 IFX-1

IFX-1 is a monoclonal anti-human C5a immunoglobulin as active pharmaceutical ingredient, which is formulated in a phosphate buffered saline and Polysorbate 80.

IFX-1 will be supplied in 10 mL glass vials at a concentration of 10 mg/mL (i.e., 100 mg per vial) for iv administration and will have the following composition:

Ingredient	Strength
IFX-1	10 mg/mL
Sodium chloride	150 mM
Sodium phosphate	10 mM
Polysorbate 80	0.05%

#### 5.1.2 Placebo

Placebo will be supplied in 10 mL glass vials for iv administration and will have the following composition:

Ingredient	Strength
Sodium chloride	150 mM
Sodium phosphate	10 mM
Polysorbate 80	0.05%

The placebo vials and content have the same appearance as the IFX-1 vials and additives.

---

## 5.2 Packaging and Labeling

The IMP will be packaged in cardboard boxes and labeled in accordance with all legal requirements.

The cardboard boxes will be labeled with a unique number (“medcode”). The glass vials containing the IMP will be labeled with the same medcode as the cardboard box in which they are packed.

The labels are part of the Clinical Trial Application documentation.

## 5.3 Supply, Storage, and Accountability

### 5.3.1 Supply

The IMP will be supplied to study sites on behalf of the sponsor by Almac. The IMP should be shipped at a temperature of 2°C to 8°C, and should not be frozen. For each subject, the IMP will be sent from Almac to the study site after the subject has been enrolled into the study at Screening. Because it may take up to 10 days for the IMP to reach the study site, at least 10 days should be allowed between Screening and first administration of IMP.

At each study site, authorized personnel will check the IMP for any loss, damage, or tampering and confirm receipt. Records of the receipt of IMP have to be maintained.

Any technical complaints arising from defects in the quality of the IMP, or defects in the packaging or labeling of the IMP, must be reported to the sponsor or the delegate at the earliest opportunity and the IMP should not be used.

The authorized personnel will be responsible for adequate handling of the IMP and local drug accountability as well as recording of the accurate administration of the IMP (i.e., complete administration of IMP, including flushing of the infusion line) used for each subject.

### 5.3.2 Storage

The IMP must be stored between 2 and 8°C and should not be frozen.

To record the temperature, an established and validated local temperature management system with temperature logs should be used. If this is not possible, the responsible site personnel will maintain temperature records for the entire duration of the study. A template for the temperature records will be provided by the Clinical Research Organization (CRO). At a minimum, the daily (working day) minimum and maximum temperatures must be documented.

All IMP supplies must be stored separately from normal hospital inventories, in a locked facility with access limited to authorized personnel.

### 5.3.3 Accountability

During the study, all IMP vials will be reconciled against the current inventory and the dispensing records as a component of the monitoring visits.

IMP administration data kept at the site will be monitored throughout the study by the monitor.

After completion of the study, all records regarding the IMP will be provided to the sponsor, who will decide on the return or destruction of any unused IMP.

In case any unused IMP should be destroyed at the site, this destruction must be documented on the form provided by the sponsor for this purpose. If unused IMP cannot be destroyed at the site, it needs to be returned to the depot.

## 5.4 Reconstitution and Administration of the Investigational Medicinal Product

### 5.4.1 Reconstitution

The IMP will be prepared in a blinded manner at the study site or site pharmacy, respectively. Depending on the dose to be administered (Table 2 and Table 3), the amount of IMP for a single infusion is 400, 800, or 1200 mg IFX-1, or placebo. IMP or placebo will be diluted in sterile sodium chloride. To keep the blinding of site personnel and subjects, the total volume in the infusion bag for each infusion should be 250 mL. Details of IMP preparation and application will be outlined in the respective IMP manual.

### 5.4.2 Administration and Compliance

**Main Period:** after Screening, subjects will be randomized to 1 of 5 treatment cohorts in a ratio of 1:1:1:1:1 (Section 5.5) and then receive IMP in the 16-week Main Period as shown in Table 2.

**Table 2 Dosing Schedule by Cohort in Main Period (Double-Blind)**

	Induction Phase				Maintenance Phase							
Visit	V2	V3	V4	V5	V6	V7	V8	V9	V10	V11	V12	
Week	0	0	1	2	4	6	8	10	12	14	16	
Day	1	4	8	15	29	43	57	71	85	99	113	
Cohort 1 (Placebo)	P	P	P	P	P	P	P	P	P	P	P	
Cohort 2 (400 mg q4w)	400	400	P	P	400	P	400	P	400	P	400	
	Cumulative IFX-1 dose: 2000 mg											
Cohort 3 (800 mg q4w)	800	800	800	P	800	P	800	P	800	P	800	
	Cumulative IFX-1 dose: 4800 mg											
Cohort 4 (800 mg q2w)	800	800	800	800	800	800	800	800	800	800	800	
	Cumulative IFX-1 dose: 8000 mg											
Cohort 5 (1200 mg q2w)	800	800	800	1200	1200	1200	1200	1200	1200	1200	1200	
	Cumulative IFX-1 dose: 10,800 mg											

HiSCR = Hidradenitis Suppurativa Clinical Response; IMP = investigational medicinal product; P = infusion of placebo; q2w = every two weeks; q4w = every four weeks; V = scheduled visit for all subjects.

400, 800, or 1200 = infusion of 400, 800, or 1200 mg IFX-1.

NOTE: cumulative doses refer to the amount of IFX-1 (doses marked in bold) received at the time the primary efficacy endpoint is assessed at Week 16 (percentage of subjects with a response, as measured by HiSCR [Section 8.2.2.2]), before administration of IMP at Week 16.

---

**Extension Period:** at Week 20 (Day 141) (HiSCR responders) or at Week 18 (Day 127) (HiSCR non-responders), subjects will receive the first administration of IMP during the 28-week Extension Period, as shown in [Table 3](#).

Subjects who are HiSCR responders at Week 16 (response on the basis of HiSCR is defined in Section [8.2.2.2](#)) will receive IFX-1 at a dose of 800 mg q4w during the Extension Period, starting at Week 20 through Week 40 (Day 141 to Day 281). If they have a loss of response (see [Definitions of Terms](#)) during the Extension Period, they will have an optional visit 2 weeks later. Subjects who still have a loss of response at the subsequent (planned) visit will be discontinued from the study and will not switch to the non-responder schedule.

Subjects who are HiSCR non-responders at Week 16 (response on the basis of HiSCR is defined in Section [8.2.2.2](#)) will receive IFX-1 at a dose of 800 mg during an Induction Phase at Weeks 18 and 19 (Day 127 and Day 130), followed by IFX-1 at a dose of 800 mg q2w during the remaining Extension Period starting from Week 20 through Week 40. The additional infusions will be administered during interim visits to the study site, starting at Week 22. Subjects who experience WOAI (see [Definitions of Terms](#)) at 2 consecutive visits during the Extension Period will be discontinued from the study.

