	
Extension Period (28 weeks) – HiSCR responders
 
Subjects from all cohorts who are HiSCR responders at Week 16 will receive IFX-1 at a dose of 800 mg q4w, starting at Week 20 through Week 40. If they have a loss of response (see Definitions of Terms) during the Extension Period, they will have an optional visit 2 weeks later. Subjects who then have a loss of response at the subsequent (planned) visit will be discontinued from the study and will not switch to the non-responder schedule.
 
Extension Period (28 weeks) – HiSCR non-responders
 
Subjects from all cohorts who are HiSCR non-responders at Week 16 will receive IMP during an Induction Phase (Weeks 18 and 19), followed by IFX-1 at a dose of 800 mg q2w during the Maintenance Phase.
 
Cohort 1:
 
 
• Induction Phase: infusion of IFX-1 800 mg at Weeks 18 (Days 127 and 130) and 19
 
• Maintenance Phase: IFX-1 800 mg at Week 20 and every other week through Week 40
 
 
Cohort 2:
 
 
• Induction Phase: infusion of IFX-1 800 mg at Week 18 (Day 127), placebo at Week 18 (Day 130), and IFX-1 800 mg at Week 19
 
• Maintenance Phase: IFX-1 800 mg at Week 20 and every other week through Week 40
 
 
Cohorts 3, 4, and 5:
 
 
• Induction Phase: infusion of IFX-1 800 mg at Week 18 (Day 127), and placebo at Week 18 (Day 130) and Week 19
 
• Maintenance Phase: IFX-1 800 mg at Week 20 and every other week through Week 40
 
 
Subjects who experience Worsening or Absence of Improvement (WOAI) (see Definitions of Terms) at 2 consecutive visits during the Maintenance Period of the Extension Period will be discontinued from the study.

Study duration	
The study duration for an individual subject will be up to 48 weeks and includes the following study periods:
 
 
• Screening Period: up to 18 days before first administration of IMP (Week -4 to Week -2 [Day -28 to Day -10])
 
• Main Period: starts with the first infusion of IMP on Week 0 (Day 1) and ends at Week 16 (Day 113), after administration of IMP
 
• Extension Period: starts after administration of IMP at Week 16 and ends at Week 44
 

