**Table 3 Dosing Schedule by Cohort in Extension Period**

	Induction Phase (Double-Blind)			Maintenance Phase (Open-Label from Week 20 Onwards)										
HiSCR Responders at Week 16 (800 mg q4w)														
Visit	-	-	-	V1R	-	V2R	-	V3R	-	V4R	-	V5R	-	V6R
Week	18		19	20	22	24	26	28	30	32	34	36	38	40
Day	127	130	134	141	155	169	183	197	211	225	239	253	267	281
Cohort 1	-	-	-	800	-	800	-	800	-	800	-	800	-	800
Cohort 2	-	-	-	800	-	800	-	800	-	800	-	800	-	800
Cohort 3	-	-	-	800	-	800	-	800	-	800	-	800	-	800
Cohort 4	-	-	-	800	-	800	-	800	-	800	-	800	-	800
Cohort 5	-	-	-	800	-	800	-	800	-	800	-	800	-	800

	Induction Phase (Double-Blind)			Maintenance Phase (Open-Label from Week 20 Onwards)										
HiSCR-Non-Responders at Week 16 (800 mg q2w)														
Visit	V1NR	V2NR	V3NR	V4NR	V5NR	V6NR	V7NR	V8NR	V9NR	V10NR	V11NR	V12NR	V13NR	V14NR
Week	18		19	20	22	24	26	28	30	32	34	36	38	40
Day	127	130	134	141	155	169	183	197	211	225	239	253	267	281
Cohort 1	800	800	800	800	800	800	800	800	800	800	800	800	800	800
Cohort 2	800	P	800	800	800	800	800	800	800	800	800	800	800	800
Cohort 3	800	P	P	800	800	800	800	800	800	800	800	800	800	800
Cohort 4	800	P	P	800	800	800	800	800	800	800	800	800	800	800
Cohort 5	800	P	P	800	800	800	800	800	800	800	800	800	800	800

HiSCR = Hidradenitis Suppurativa Clinical Response; V = scheduled visit for all subjects; VxNR = scheduled visit for HiSCR non-responders at Week 16; VxR = scheduled visit for HiSCR responders at Week 16.

800 = infusion of 800 mg IFX-1, P = infusion of placebo.

---

During the Main Period and the Extension Period, the IMP (IFX-1 or placebo) will be administered by the responsible personnel at the site:

- The IMP will be infused over a period of 30 to 60 min ( $\pm$  10 min) via an iv line
- At the end of the infusion, the iv line will be briefly flushed with approximately 10 mL of sterile sodium chloride to ensure that any IMP remaining in the iv line is administered

After each of the first 2 infusions of IMP administered in the Induction Phases of the Main and Extension Periods, subjects must remain at the study site for at least 30 min after end of IMP administration; appropriate treatment for potential infusion-related reactions must be available during this time.

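### Section 5.4.2's sentence on the non-responder Extension induction contradicts the visit calendar, Table 3 and the Synopsis; no reading of it fits more than one of the five cohorts

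*Combined protocol and SAP*

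**What the plan says.** The sentence at issue is in Section 5.4.2 (Administration and Compliance), between Table 2 and Table 3. It states that non-responders "will receive IFX-1 at a dose of 800 mg during an Induction Phase at Weeks 18 and 19 (Day 127 and Day 130"), and then move to 800 mg every two weeks from Week 20.

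Table 3 follows directly. Its day row reads "Day 127 130 134 141 155", with Days 127 and 130 under Week 18 and Day 134 under Week 19. Its key is "800 = infusion of 800 mg IFX-1, P = infusion of placebo". In the non-responder block, Cohort 1 has 800 at all three induction visits, Cohort 2 reads "Cohort 2 800 P 800 800", and Cohort 3 reads "Cohort 3 800 P P 800". Cohorts 4 and 5 are the same as Cohort 3.

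The Synopsis gives the same schedule in words. For Cohort 1 it has "infusion of IFX-1 800 mg at Weeks 18 (Days 127 and 130) and 19". For Cohorts 3 to 5 it has "infusion of IFX-1 800 mg at Week 18 (Day 127), and placebo at Week 18 (Day 130) and Week 19".

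Sections 3.1 and 7.3 describe the induction as IMP, a term that covers placebo, and refer to Table 3. The non-responder Schedule of Assessments and the visit list in Section 7.3 both show three induction administrations: two in Week 18 and one in Week 19.

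**The concern.** Two things look wrong. The sentence pairs two weeks with two days, but both days belong to the first of those weeks. It also gives every non-responder active drug at the visits it names, whereas Table 3 and the Synopsis put placebo at some of those visits for four of the five cohorts.

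This is an operative dosing statement for a phase that Section 5.5 keeps double-blind for non-responders. Two other rules depend on which schedule is planned. Section 10.9 reports the dose received relative to the planned cumulative dose, by cohort. Section 6.2.3 discontinues subjects who omit more than two scheduled infusions in the Extension Period. Both need one unambiguous list of scheduled infusions and doses.

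**Working it through.** **Calendar.** The visit tables follow Day = 7 × Week + 1. This reproduces the plan's Week 16 as 7 × 16 + 1 = 113. Then:
- Week 18 = 7 × 18 + 1 = 127
- Week 19 = 7 × 19 + 1 = 134
- Week 20 = 7 × 20 + 1 = 141

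Day 130 is 127 + 3, the second Week 18 visit. The days in the sentence therefore do not cover Week 19.

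**Table 3 against the Synopsis.** Compared visit by visit, the two agree for all five cohorts. Induction IFX-1 is:
- Cohort 1: 800 + 800 + 800 = 2400 mg
- Cohort 2: 800 + 0 + 800 = 1600 mg
- Cohorts 3 to 5: 800 + 0 + 0 = 800 mg

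**The sentence against Table 3.** Three readings are possible: the days as printed; one infusion in each named week; and all three visits, with the day parenthesis moved to follow Week 18 as in the Synopsis text for Cohort 1. Differences are the sentence minus Table 3.

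| Reading | Active days | Total | Cohort 1 | Cohort 2 | Cohorts 3–5 |
|---|---|---|---|---|---|
| As printed | 127, 130 | 1600 mg | differs on Day 134; −800 mg | differs on Days 130 and 134; 0 mg | differs on Day 130; +800 mg |
| One per week | 127, 134 | 1600 mg | differs on Day 130; −800 mg | matches | differs on Day 134; +800 mg |
| All three visits | 127, 130, 134 | 2400 mg | matches | differs on Day 130; +800 mg | differs on Days 130 and 134; +1600 mg |

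The number of cohorts matched is 0, 1 and 1 of 5. Cohorts 3 to 5 are matched by none of the readings.

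**Planned Extension dose.** Weeks 20 to 40 hold 11 two-weekly infusions, 11 × 800 = 8800 mg. Adding the induction, Table 3 plans 11,200 mg (Cohort 1), 10,400 mg (Cohort 2) and 9600 mg (Cohorts 3 to 5). The sentence implies one figure for all cohorts: 10,400 mg under the first two readings or 11,200 mg under the third.

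**Scheduled infusions.** Table 3 has 3 + 11 = 14 per non-responder, counting placebo. The first two readings give 2 + 11 = 13, so one induction infusion that could be omitted under Table 3 would not count as scheduled.

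**The case against.** The best defence is that this is a single loose summary sentence and that the governing schedule is clear. The same section introduces the Extension dosing as shown in Table 3. Footnote (d) to the Schedules of Assessments and the administration item in Section 7.3 both send the reader there, and the Synopsis agrees with it throughout. That stands: the sentence is the outlier, although the protocol has no rule that a table overrides text.

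A reader might infer several stronger things that the documents do not support.

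- **That the text fits no cohort at all.** This holds only if the printed days are taken at face value. Moving the parenthesis makes the sentence describe Cohort 1 exactly.
- **That subjects would be misdosed by −800 to +800 mg.** That range belongs to the literal reading (the one-per-week reading happens to give the same range) and is a difference between two instructions, not an expected error. Cohorts are assigned centrally through the IRT (Section 5.5), product is prepared blinded (Section 5.4.1), vials carry medcodes (Section 5.2) and placebo looks identical (Section 5.1.2). Blinded staff could not readily exchange placebo for active drug on the strength of this sentence.
- **That a visit would be dropped or the masking lost.** The Schedule of Assessments and Section 7.3 keep all three induction visits, and the safeguards just listed protect the blind.
- **That the efficacy result is compromised.** The primary endpoint is assessed at Week 16, before these infusions (Section 10.4.1). In the Extension, each administration is recorded (Section 5.4.2), so a departure would be visible.

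None of this removes the contradiction for Cohorts 3 to 5.

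**Conclusion.** The sentence is wrong as written: it contradicts the protocol's calendar, and it is inconsistent with the cohort-specific schedule in Table 3 and the Synopsis. At best it fits one cohort of five, and for three of the five it conflicts under every reading. This is an internal inconsistency, not an arithmetic error.

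The consequence is limited. What is exposed is the definition of the planned Extension dose in Section 10.9 and the count of omitted infusions in Section 6.2.3, together with the clarity of a dosing instruction in a double-blind phase. The dose differences above assume that one reading of the sentence is applied uniformly to all non-responders. They measure the disagreement between passages and do not forecast exposure. The conclusion does not depend on which schedule the sponsor intended.

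**What to change.** Reconcile the Section 5.4.2 sentence with Table 3 and the Synopsis, and have the sponsor confirm the single intended schedule. Then replace the sentence with a reference to that schedule, correct the pairing of weeks and days, and use the term IMP as Sections 3.1 and 7.3 do. That term covers active and placebo infusions alike, so it leaves the content of each visit to the confirmed schedule. State that the planned dose in Section 10.9 and the scheduled infusions in Section 6.2.3 are taken from the same schedule.

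The cost is one replaced sentence and a short cross-reference in an amendment. If the sponsor confirms the schedule that Table 3 and the Synopsis already share, neither of those needs to change.

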**Table 3 Dosing Schedule by Cohort in Extension Period**

	Induction Phase (Double-Blind)			Maintenance Phase (Open-Label from Week 20 Onwards)										
HiSCR Responders at Week 16 (800 mg q4w)														
Visit	-	-	-	V1R	-	V2R	-	V3R	-	V4R	-	V5R	-	V6R
Week	18		19	20	22	24	26	28	30	32	34	36	38	40
Day	127	130	134	141	155	169	183	197	211	225	239	253	267	281
Cohort 1	-	-	-	800	-	800	-	800	-	800	-	800	-	800
Cohort 2	-	-	-	800	-	800	-	800	-	800	-	800	-	800
Cohort 3	-	-	-	800	-	800	-	800	-	800	-	800	-	800
Cohort 4	-	-	-	800	-	800	-	800	-	800	-	800	-	800
Cohort 5	-	-	-	800	-	800	-	800	-	800	-	800	-	800

	Induction Phase (Double-Blind)			Maintenance Phase (Open-Label from Week 20 Onwards)										
HiSCR-Non-Responders at Week 16 (800 mg q2w)														
Visit	V1NR	V2NR	V3NR	V4NR	V5NR	V6NR	V7NR	V8NR	V9NR	V10NR	V11NR	V12NR	V13NR	V14NR
Week	18		19	20	22	24	26	28	30	32	34	36	38	40
Day	127	130	134	141	155	169	183	197	211	225	239	253	267	281
Cohort 1	800	800	800	800	800	800	800	800	800	800	800	800	800	800
Cohort 2	800	P	800	800	800	800	800	800	800	800	800	800	800	800
Cohort 3	800	P	P	800	800	800	800	800	800	800	800	800	800	800
Cohort 4	800	P	P	800	800	800	800	800	800	800	800	800	800	800
Cohort 5	800	P	P	800	800	800	800	800	800	800	800	800	800	800

HiSCR = Hidradenitis Suppurativa Clinical Response; V = scheduled visit for all subjects; VxNR = scheduled visit for HiSCR non-responders at Week 16; VxR = scheduled visit for HiSCR responders at Week 16.

800 = infusion of 800 mg IFX-1, P = infusion of placebo.

---

During the Main Period and the Extension Period, the IMP (IFX-1 or placebo) will be administered by the responsible personnel at the site:

- The IMP will be infused over a period of 30 to 60 min ( $\pm$  10 min) via an iv line
- At the end of the infusion, the iv line will be briefly flushed with approximately 10 mL of sterile sodium chloride to ensure that any IMP remaining in the iv line is administered

After each of the first 2 infusions of IMP administered in the Induction Phases of the Main and Extension Periods, subjects must remain at the study site for at least 30 min after end of IMP administration; appropriate treatment for potential infusion-related reactions must be available during this time.

For France: After each infusion of IMP administered in the Induction Phases of the Main and Extension Periods, subjects must remain at the study site for at least 60 min after end of IMP administration; appropriate treatment for potential infusion-related reactions must be available during this time.

Each administration of IMP will be recorded in detail in the source documentation and in the eCRF.

If a subject misses a visit for a scheduled infusion of IMP for any reason, the infusion must be administered as soon as possible after the scheduled time of infusion. If the scheduled infusion cannot be administered within 3 days after the scheduled time of infusion, then that infusion should be omitted and the subsequent infusion must be administered as planned.

If a subject appears at the study center for a scheduled infusion but the infusion cannot be administered due to any reason, the visit can be repeated within 3 days (if the investigator thinks that the IMP can be administered within 3 days). Otherwise, the infusion will be omitted and is documented accordingly in the eCRF.

Subjects who omit more than 2 scheduled (consecutive or non-consecutive) infusions during the Main Period will be discontinued from the study and will have a Post-Treatment FUV 3 months after discontinuation or when another HS therapy has been started (Section 6.2).

The number of unused, partially used, and empty vials will be documented and the vials will be kept until the drug accountability documentation has been checked by the monitor.

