*Meningitis/meningococcal septicemia:* current data do not suggest that subjects treated with IFX-1 are at significantly increased risk of infection with *N. meningitides* and to date, no cases of meningitis or meningococcal septicemia have been reported in clinical studies with IFX-1. Therefore, mandatory vaccination or concomitant broad spectrum antibiotic treatment is not warranted based on the mode of action for IFX-1. However, until a larger number of subjects have been exposed to IFX-1, investigators should be vigilant for signs of *N. meningitides* infection. See Section [5.6](#) for the procedures to be followed in case of meningitis/meningococcal septicemia.

*Anaphylactic reactions and acute systemic allergic hypersensitivity:* because IFX-1 is an antibody/protein, a general risk for anaphylactic reactions and acute systemic allergic hypersensitivity exists. Subjects who are included in this study are treated with IFX-1 at the study site so that adequate treatment and care is available in case of an anaphylactic reaction. To date, no anaphylactic reactions have been reported after administration of IFX-1 in clinical Phase I and II studies. See Section [5.6](#) for the procedures to be followed in case of anaphylactic reactions and acute systemic allergic hypersensitivity.

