### Extension Period (28 Weeks) – HiSCR Responders

Subjects from all cohorts who are HiSCR responders at Week 16 (response on the basis of HiSCR is defined in Section 8.2.2.2) will receive IFX-1 at a dose of 800 mg q4w, starting at Week 20 through Week 40. Subjects who have a loss of response (see [Definitions of Terms](#)) during the Extension Period will have an optional visit 2 weeks later. Subjects who then have a loss of response at the subsequent (planned) visit will be discontinued from the study.

A final visit at the study site for efficacy, PK, PD, and safety assessments will occur at Week 44. For subjects who discontinue early, a Post-Treatment Follow-Up visit will occur 3 months after the early discontinuation or when another HS therapy has been started, whichever occurs first. At the Post-Treatment Follow-Up visit the same parameters for efficacy, PK, PD and safety as at Week 44 or the early discontinuation visit will be assessed.

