**Infusion-Related Reactions/Anaphylactic Reactions and Acute Systemic Allergic Hypersensitivity:** In case of any severe, acute systemic hypersensitivity reaction during, or shortly after, infusion of IFX-1, the infusion should be stopped immediately and the subject discontinued from further dosing. In such cases, subjects should be closely monitored for any changes in blood pressure, heart rate, metabolic conditions, or organ function, and appropriate measures should be taken to stabilize all vital signs. Fluid resuscitation may be needed, as well as vasopressor therapy or other measures to treat changes in blood pressure, vital signs, or metabolic conditions in general. In cases of emergency with immediate life-threatening potential such as cardiac arrest or similar life-threatening changes, appropriate cardio-pulmonary resuscitation should be started immediately according to applicable guidelines, or as established at the study sites through existing standard operating procedures or other algorithms for cardio-pulmonary resuscitation according to current recommended resuscitation guidelines.

---

For any potential infusion-related event, the physician should check for a potentially developing or existing anaphylactic reaction. In case an anaphylactic reaction is anticipated, appropriate immediate actions should be taken according to the severity or stage of the detected anaphylactic reaction as recommended by existing guidelines for the treatment of anaphylactic reactions or, if established at the study sites, according to available standard operating procedures or algorithms.

If the investigator abstains from further dosing, the subject should be discontinued from the study and handled as drop-out.

In case of an emergency or other situation in which it is medically imperative for the investigator to identify the IMP that a subject has received or is receiving during the Main Period and during the Induction Phase of the Extension Period, the procedure for emergency identification of IMP described in Section 5.5 must be followed.

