## **10.11 Interim Analysis**

No formal interim analysis is planned for this study. The database will be locked for the analysis of the Main Period when all data up to and including Week 16 have been collected and cleaned, and the BDRM has taken place. All endpoints in the Main Period will be analyzed after unblinding, which will take place after all subjects have completed the assessments at Week 20 due to operational reasons. A database snapshot will be performed during the Extension

---

Period. A second database lock will be performed after all data of the Extension Period have been collected and cleaned, and the corresponding analyses of endpoints will be performed.

An independent, unblinded Data Monitoring Committee (DMC) will receive data for safety reviews at prespecified time points in order to detect and report early evidence of unanticipated harm to subjects (see Section 13.3). To maintain the blind, the data for the safety reviews will be delivered by an unblinded CRO biostatistics team located at a different geographical site to the blinded CRO biostatistics personnel involved in the study.

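### Placebo responders receive their first IFX-1 infusion at Week 20 with no mandated post-infusion stay, because Section 5.4.2 ties the stay to Induction Phases that responders do not have

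*Combined protocol and SAP*

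**What the plan says.** **The stay rule.** After Table 3, Section 5.4.2 requires at least 30 minutes on site, and its wording limits this to "first 2 infusions of IMP administered in the Induction Phases of the Main and Extension Periods, subjects must remain at the study site". The country rule begins "For France: After each infusion of IMP administered in the Induction Phases of the Main and Extension Periods" and sets 60 minutes. Both depend on the Induction Phase label.

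**Who has an Induction Phase in the Extension Period.** Section 5.4.2 separates the two groups: "at Week 20 (Day 141) (HiSCR responders) or at Week 18 (Day 127) (HiSCR non-responders), subjects will receive the first administration of IMP". Section 3.1 says that responders from all cohorts "will receive IFX-1 at a dose of 800 mg q4w, starting at Week 20 through Week 40", and gives the Week 18 and 19 Induction Phase to non-responders only. The responder block of Table 3 has dashes at Weeks 18 and 19, and the responder Schedule of Assessments shows only a Maintenance Phase.

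**What Cohort 1 has had by then.** Table 2 shows placebo at every Main Period infusion, including Week 16.

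**The risk the plan names.** Section 1.4.2 states that "because IFX-1 is an antibody/protein, a general risk for anaphylactic reactions and acute systemic allergic hypersensitivity exists", and adds: "Subjects who are included in this study are treated with IFX-1 at the study site so that adequate treatment and care is available". Section 5.6 anticipates such events: "In case of any severe, acute systemic hypersensitivity reaction during, or shortly after, infusion of IFX-1".

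**Unblinding.** Section 10.11 places the Main Period analysis after "unblinding, which will take place after all subjects have completed the assessments at Week 20 due to operational reasons".

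**The concern.** A post-infusion stay makes most sense at a subject's first exposures to the antibody. The rule achieves this in every group except one. A placebo responder has two observed infusions in the Main Period, both placebo, and then a first dose of 800 mg IFX-1 with no required observation.

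What is at stake is the timing of care. A reaction that starts soon after the infusion ends could begin once the subject has left, and treatment could be delayed. The event would still be recorded as an adverse event, so this is a matter of subject safety and not of the efficacy analysis.

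**Working it through.** **1. Check the reading of Table 2.** The IFX-1 received before the Week 16 infusion reproduces the protocol's cumulative doses:
- Cohort 2: 5 × 400 = 2000 mg
- Cohort 3: 6 × 800 = 4800 mg
- Cohort 4: 10 × 800 = 8000 mg
- Cohort 5: 3 × 800 + 7 × 1200 = 10,800 mg
- Cohort 1: 0 mg, and the Week 16 infusion is also placebo

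**2. Set first IFX-1 exposure against the stay rule** (Tables 2 and 3).

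| Group | First two IFX-1 infusions | Phase | Stay mandated? |
|---|---|---|---|
| Cohorts 2 to 5 | Days 1 and 4 | Main Period Induction | Yes |
| Cohort 1 non-responders | Days 127 and 130 | Extension Induction | Yes |
| Cohort 1 responders | Days 141 and 169 | Extension Maintenance | No |

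**3. Look for another provision that closes the gap.**
- Section 1.4.2 relies on treatment at the site but gives no observation time.
- Section 5.6 says how to manage a reaction, not how long to watch for one.
- Section 9.5 requires resuscitation means but no stay.
- The responders' Week 20 IFX-1 sample is drawn before dosing (footnote c of the Schedules). The only post-infusion sample in the Extension Period is for non-responders on Day 130.

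**4. Count the subjects.** Inputs from Section 10.2 are 35 randomized and at least 29 evaluable per cohort, with assumed Week 16 HiSCR rates of 25%, 30%, 45%, 55% and 60%.
- Cohort 1 responders: 0.25 × 29 = 7.25; 0.25 × 35 = 8.75. The central 95% binomial ranges are 3 to 12 and 4 to 14.
- All responders: 0.25 + 0.30 + 0.45 + 0.55 + 0.60 = 2.15; 2.15 × 29 = 62.35; 2.15 × 35 = 75.25.
- Non-responders in Cohorts 2 to 5, who receive placebo on Day 130 and must stay: 0.70 + 0.55 + 0.45 + 0.40 = 2.10; 2.10 × 29 = 60.9; 2.10 × 35 = 73.5.

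As written, about 61 to 74 subjects who have already had IFX-1 stay after a placebo infusion, while about 7 to 9 subjects new to the antibody need not stay after their first dose.

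**The case against.** **The risk is theoretical so far.** Section 1.4.2 reports no anaphylaxis with IFX-1 in Phase I or II, and 48 + 82 + 12 = 142 Phase II subjects had been treated. This belongs in any fair statement of the risk. It does not explain the gap, because the sponsor had the same data when it required a stay at the other first exposures. Zero events in 142 also leaves a one-sided 95% upper limit of 1 − 0.05^(1/142), about 2.1%, if the populations and doses are pooled.

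**Other safeguards remain.** Site staff give the infusion over 30 to 60 minutes, Section 5.6 calls for close monitoring when a side effect is suspected, and an investigator may keep a subject longer. The IMP manual, which is not among the documents, might add a stay. This limits the gap to the fixed minimum time but does not close it.

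**The Day 130 comparison has an explanation.** The Extension Induction Phase is double-blind, and Cohort 1 non-responders receive IFX-1 that day, so a uniform stay is needed. That is correct. The 61 to 74 subjects show where the rule falls; their stays are not themselves a defect.

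**That sites do not know the cohort at Week 20 is an inference.** Section 10.11 concerns unblinding for the Main Period analysis, and Section 5.5 does not say what sites know about responders at that visit. The inference is reasonable, since nothing in the plan gives sites the allocation earlier outside emergencies.

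**The remedy is wider than the defect.** Responders in Cohorts 2 to 5 have already had IFX-1 and account for 1.90/2.15, about 88%, of the added stays (1.90 × 29 × 2 = 110 to 1.90 × 35 × 2 = 133). This is a real cost, and the price of a rule that does not depend on knowing the cohort.

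**Conclusion.** The concern holds. As written, Section 5.4.2 mandates a stay at the first two IFX-1 infusions in every group except Cohort 1 responders, whose first two have none. About 7 to 9 subjects are affected. That count assumes the protocol's 25% placebo response, that between 29 and 35 Cohort 1 subjects reach Week 16, and that all responders continue to the Week 20 infusion. The documents give no reaction rate beyond none reported, so the clinical consequence cannot be quantified.

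The gap is small and procedural, with no effect on alpha, power, sample size or the primary endpoint. It should still be fixed: the rule misses a first exposure of the kind it protects elsewhere, and the correction is cheap.

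**What to change.** Define the general rule by Period instead of by phase, for example: *subjects stay on site for at least 30 minutes after each of their first two infusions in the Main Period and each of their first two infusions in the Extension Period.* For non-responders nothing changes (Days 127 and 130). For responders it adds Weeks 20 and 24 (Days 141 and 169). Apply it to responders from all cohorts, so that no site needs to know the allocation.

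In the French rule, add a 60-minute stay after the same two responder infusions and keep the existing stay after every Induction Phase infusion.

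**Cost.** Two sentences of text, and two extra stays for about 62 to 75 responders: 2 × 62.35 = 124.7 to 2 × 75.25 = 150.5, or about 125 to 150 stays of 30 minutes (60 in France). No visit, sample or drug is added. Limiting the change to Week 20 would halve this, but placebo responders would then have one observed IFX-1 infusion where every other group has two.
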